10.2 Secondary Efficacy Analyses

10.2.1 Secondary Analyses of Primary Efficacy Endpoint

Our primary analysis population will be the per-protocol population because of the non-inferiority design. The secondary analysis population will be the intention-to-treat analysis.

10.2.2 Analyses of Secondary Endpoints

- Treatment failure defined as an incomplete resolution of the clinical signs and symptoms associated with the AECOPD at day 30 after inclusion of the study (i.e not reaching the baseline condition prior to the AECOPD) scored using the modified Anthonisen criteria.
 - Dichotomous variable (yes/no)
 - Description: Number and percentage
 - Test: logistic mixed-effects model
- Change in quality of life using the COPD assessment test
 - Measurements are continuous and paired (multiple (3) measurements in all patients (day 1, 10 and 30))
 - Description:
 - Normal distribution: mean score \pm SD
 - Skewed distribution: median (IQR)
 - Test:
 - mixed effects model with random effects for center and patient to account for the extra hierarchical level in the data. In case of violations of the normality assumptions, transformations of the dependent variable will be applied or the bootstrapping procedure will be used to obtain robust confidence intervals.
 - MCID = a decrease of 2 points after treatment is considered a minimal clinically important difference. When the difference in improvement of the CAT is < 2 points, then this will be considered a clinically non-significant difference[16,17].

- EXACT – Respiratory symptoms scale
 - Measurements are continuous and paired (multiple (3) measurements in all patients (day 1, 10 and 30))
 - Description:
 - Normal distribution: mean score \pm SD
 - Skewed distribution: median (IQR)
 - Test:
 - mixed effects model with random effects for center and patient to account for the extra hierarchical level in the data. In case of violations of the normality assumptions, transformations of the dependent variable will be applied or the bootstrapping will be used to obtain robust confidence intervals.
 - MCID: symptomatic improvement is defined by a decrease of the RS-total score of at least 2 points. When the difference in improvement of the EXACT is < 2 points, then this will be considered a clinically non-significant difference[18].

- Time to complete resolution of symptoms in days according to daily symptom diaries evaluating the modified Anthonisen criteria
 - Continuous variable, unpaired
 - Description:
 - Normal distribution: mean score \pm SD
 - Skewed distribution: median (IQR)
 - Test: mixed-effects model

- Decision to start antibiotic treatment after an initial opposite decision (after 48 hours)
 - Dichotomous variable (yes/no)
 - Description: Number and percentage
 - Test: logistic mixed-effects model.

- Non-Invasive ventilation after 72 hours of admission
 - Dichotomous variable (yes/no)
 - Description: Number and percentage
 - Test: logistic mixed-effects model.

- Length of hospitalization in days
 - Continuous variable, unpaired
 - Description:
 - Normal distribution: mean score \pm SD
 - Skewed distribution: median (IQR)
 - Test: mixed-effects model

- Re-exacerbation within 30 days
 - Dichotomous variable (yes/no)
 - Description: Number and percentage
 - Test: logistic mixed-effects model.

- Side effects (gastro-intestinal complaints, allergic reactions)
 - Nominal/dichotomous variable (yes/no), unpaired
 - Description: Number and percentage
 - Test: logistic mixed-effects model.

- Cumulative antibiotic consumption in days
 - Continuous variable, unpaired
 - Description:
 - Normal distribution: mean score \pm SD
 - Skewed distribution: median (IQR)
 - Test: mixed-effects model

- Cumulative prednisolone consumption in days
 - Continuous variable, unpaired
 - Description:
 - Normal distribution: mean score \pm SD
 - Skewed distribution: median (IQR)
 - Test: mixed-effects model

11 Safety Analyses

All (serious) adverse events reported spontaneously by the subject or observed by the investigator or his staff from the moment of informed consent until the end of the 30 days of follow-up will be recorded. Suspected unexpected serious adverse reactions will also be recorded.

We will list the following (serious) adverse reactions:

- Mortality
 - With a description of the frequencies and percentage in both groups
 - Analysis will be done using Chi square's test or Fisher's exact test, depending on the number of deaths.

- (Serious) adverse reactions
 - With a description of the frequencies and percentage in both groups
 - Analysis will be done using Chi square's test or Fisher's exact test, depending on the number of reactions/events.

Serious adverse events will be summarized as in the table below:

Table 3. Summary of all (serious) adverse events

Outcome measure	Usual care			PCT-guided treatment			(adjusted) odds ratio or relative risk	95% confidence interval	
	n	freq.	%	n	freq.	%		lower limit	upper limit
Mortality									
Adverse effects from antibiotics - Allergic reaction - Diarrhea - Clostridium difficile infection									
Readmission, overall									
Readmission, with AECOPD									
Pneumonia									
ICU-admission									

When calculating the incidence of adverse events, or any sub-classification thereof by treatment, time period, severity, etc., each subject will only be counted once and any repetitions will be ignored; the denominator will be the total population size.

Per ClinicalTrial.gov reporting requirements, three tables summarizing adverse events are required:

- All-Cause Mortality: A table of all anticipated and unanticipated deaths due to any cause, with number and frequency of such events in each arm/group of the clinical study.

Table 4. All-Cause Mortality

Outcome measure	Usual care			PCT-guided treatment			(adjusted) odds ratio or relative risk	95% confidence interval	
	n	freq.	%	n	freq.	%		lower limit	upper limit
All-cause mortality									

- Serious Adverse Events:

Table 5. Serious Adverse Events

Type of SAE	Usual care			PCT-guided treatment			(adjusted) odds ratio or relative risk	95% confidence interval	
	n	freq.	%	n	freq.	%		lower limit	upper limit
Respiratory system: - Pneumonia - Respiratory failure/need for NIV									
Cardiovascular system: - myocardial infarction - acute heart failure									
Gastro-intestinal system - severe diarrhea									

- Other (Not Including Serious) Adverse Events: A table of anticipated and unanticipated events (not included in the serious adverse event table) that exceed a frequency threshold (for example, 5 %) within any arm of the clinical study, grouped by organ system, with number and frequency of such events in each arm/group of the clinical study.

Table 6. Other (Not Including Serious) Adverse Events

Outcome measure	Usual care			PCT-guided treatment			(adjusted) odds ratio or relative risk	95% confidence interval	
	n	freq.	%	n	freq.	%		lower limit	upper limit
Respiratory system - Need for more intensive use of nebulizer									
Cardiovascular system - Hypertension									
Gastrointestinal system									

- Diarrhea									
- constipation									

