8.3 Covariates and Subgroups

(ICH E3; 9.7.1, 11.4.2.1. ICH E9; 5.7)

As mentioned above, patients will be randomized. This will remove the effect of possible confounders.

The randomization and treatment allocation will be stratified by center. We will use alternating blocks of 4 and 6 patients which will lead to a maximum imbalance of 3 participants per center. We consider this to be an acceptable amount of imbalance.

At this moment we do not have the intention to analyze subgroups. We do not exclude the possibility of exploratory subgroup analysis but these results can only be presented as summary statistics.

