8.6 Multiple Testing

Op dit moment niet van toepassing, mogelijk nog wanneer primair eindpunt zou veranderen.

9 Summary of Study Data

Table 1. Baseline characteristics

The baseline characteristics are given in the table below.

	Usual care (n = 308)	PCT-guided treatment (n = 308)
Age in years – mean±SD		
Male gender – no. (%)		
BMI – mean±SD		
Smoking status: - current – no. (%) - past – no. (%) - pack years (mean, range)		
FEV1 % predicted - mean±SD		
GOLD classification: - I – no. (%) - II – no. (%) - III – no. (%) - IV – no. (%)		
Exacerbation type: - type I – no. (%) - type II – no. (%) - type III – no. (%)		
Median duration of symptoms in days - mean±SD		
CRP in mg/L – median [IQR]		
WBC 10 ⁹ /L – mean±SD		
CAT score – median [IQR]		
EXACT- RS score – median [IQR]		

Primary outcome

The primary outcome will be treatment failure within 30 days. A non-inferiority margin of 5% will be used to assess non-inferiority. Treatment failure is defined as disease-related mortality, endotracheal intubation, vasopressors, renal failure, lung abscess/empyema, development of pneumonia and hospital readmission within 30 days.

- Binary outcome parameter: yes or no. Description: number and percentage.
- To account for the multicenter effect a logistic mixed effects model will be estimated with

centers as random effect and treatment group as fixed effect to analyze the primary outcome. The risk of primary endpoint in the PCT guided treatment arm versus the usual care treatment arm will be reported with an odds ratio from the logistic model, with a 95% confidence interval. Based on this CI we will determine non-inferiority of the treatment.

Secondary outcome parameters

Skewed data will be analyzed using non-parametric tests. Paired measurements will be analyzed using paired tests.

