The quality of life endpoints, using the COPD Assessment Test (CAT) and the EXACT-respiratory symptoms questionnaire, consist of multiple (three) measurements per subject. These measurements are all performed on the same time point (baseline, day 10 and day 30). These endpoints will be scored using the mean score and standard deviation when normally distributed and a median with the inter quartile range when the data have a skewed distribution. These data will be analyzed with a mixed effects model with random effects for center and patient to account for the extra hierarchical level in the data. The residuals will be evaluated for normality to test the assumptions of the models. In case of violations, transformations will be conducted on the dependent variable.

The unpaired continuous variables will be reported using the mean score and the standard deviation (normal distribution) or the median with the inter quartile range (skewed distribution). These variables will be analyzed using an mixed effects model.

The frequency and percentage will be reported for the categorical (mostly dichotomous) variables. Analysis of these variables will be performed using a logistic mixed-effects model.

- The analysis populations upon which the tables and figures will be based will be the per-protocol analysis population.

Table 2. Primary endpoint and secondary endpoints

	PCT-guided treatment (n = 315)	Usual care (n = 315)		p-value
Primary endpoint:				
Overall treatment failure:	n (%)	n (%)	OR (95% CI)	
- Disease-related mortality	n (%)	n (%)		
- Endotracheal intubation	n (%)	n (%)		
- Vasopressors	n (%)	n (%)		
- Renal failure	n (%)	n (%)		
- Lung abscess/empyema	n (%)	n (%)		
- Pneumonia development	n (%)	n (%)		
- Hospital readmission	n (%)	n (%)		
Secondary endpoints				
Incomplete resolution of the clinical signs and symptoms at day 30 after (scored using the modified Anthonisen criteria)	n (%)	n (%)	OR (95% CI)	

Change in QoL using the CAT: after 10 days after 30 days	mean (SD)or median [IQR]	mean (SD)or median [IQR]		
Start of antibiotic therapy after an initial opposite decision (after 48 hours)	n (%)	n (%)	OR (95% CI)	
Side effects (gastro-intestinal complaints, allergic reactions)	n (%)	n (%)	OR (95% CI)	
Cumulative antibiotic consumption	mean/median days (SD) or [IQR]	mean/median days (SD) or [IQR]		
Cumulative prednisolone consumption	mean/median days (SD) or [IQR]	mean/median days (SD) or [IQR]		

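### For CAT and E-RS the SAP names no fixed effects, baseline adjustment or single outcome scale, so precision may be lost and the 2-point rule may be applied to an estimate it does not fit

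*SAP*

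**What the plan says.** - **Model.** SAP section 9 (secondary outcome parameters), the opening of section 10, and section 10.2.2 cover CAT and E-RS. Section 9 says that these endpoints "consist of multiple (three) measurements per subject", namely baseline, day 10 and day 30. Section 10.2.2 describes both as "Measurements are continuous and paired (multiple (3) measurements in all patients (day 1, 10 and 30" and names as the test a "mixed effects model with random effects for center and patient to account for the extra hierarchical level in the data". No arm, visit, arm-by-visit or admission-score term is written down, and no constraint on the baseline means.
- **Covariates.** SAP 8.3 names no covariate. It says of randomisation: "This will remove the effect of possible confounders".
- **Competing rules.** Two general sentences in SAP 9 stand before the endpoint-specific text: "Skewed data will be analyzed using non-parametric tests" and "Paired measurements will be analyzed using paired tests". Protocol section 10 (Secondary analyses) assigns continuous secondary endpoints to an unpaired t-test or a Mann-Whitney U test.
- **Non-normal residuals.** SAP 9 gives one remedy, "In case of violations, transformations will be conducted on the dependent variable", and section 10 repeats it. SAP 10.2.2 says that "transformations of the dependent variable will be applied", or alternatively that bootstrapping will supply robust confidence intervals. It gives no rule for choosing.
- **Threshold and reporting.** SAP 10.2.2 calls a between-arm difference in improvement of less than 2 points clinically non-significant, for CAT and for E-RS. SAP Table 2 lists the change after 10 and after 30 days but leaves the effect-estimate column empty for both scales.

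**The concern.** Improved quality of life is a stated secondary objective (Protocol section 2, SAP 5.1), and the SAP fixes in advance how large a CAT difference must be to count. That rule works only if the model returns the arm difference at a stated visit, in points. The text as written fits several models. One gives that difference with less precision than the collected data allow. One gives a quantity that mixes in the pre-treatment score and is smaller. One gives an estimate that is not in points. The choice would then be made after the data are seen, and the clinical label could depend on it.

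**Working it through.** **The plan's own figure.** The documents contain no design calculation for CAT or E-RS. The only one is for the primary endpoint (SAP 7), and it reproduces. With failure rates of 20.4% and 16.7%, margin 5 points, one-sided alpha 0.025 and 80% power:

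n = (1.960 + 0.8416)² × (0.204×0.796 + 0.167×0.833) / (0.05 + 0.037)² = 7.849 × 0.3015 / 0.007569 = 312.7, so 313 per arm.

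At one-sided alpha 0.0246 (half of the 0.0492 in SAP 8.5.5) the result is 315 per arm. I use n = 315 below.

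**Inputs that the documents do not give.** The SD of the scores and the within-patient correlation rho are assumptions: SD 7 (range 6 to 8) and rho 0.3 to 0.8. I also assume equal variances at all visits, complete data and no centre effect.

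**Formulas for the arm difference at one visit**
- Free baseline means (change score): Var = 2·SD²·(1−rho)·(2/n)
- Admission score as covariate: Var = SD²·(1−rho²)·(2/n)
- Ratio of the second to the first: (1−rho²) / [2(1−rho)] = (1+rho)/2
- Extra patients needed without adjustment: 2/(1+rho) − 1

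Example at SD 7, rho 0.5:
- Change score: 2×49×0.5×2/315 = 0.311, SE 0.558.
- Adjusted: 49×0.75×2/315 = 0.233, SE 0.483.

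**Three fixed-effect structures that the text allows.** These were computed by generalised least squares with a random patient intercept and three visits. The true effect is −2 points at days 10 and 30 and zero at baseline.

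| rho | Arm-by-visit, free baseline: estimate (SE) | Arm-by-visit, common baseline mean: estimate (SE) | Visit plus one arm effect over three visits: estimate (SE) |
|---|---|---|---|
| 0.3 | −2.00 (0.660) | −2.00 (0.532) | −1.33 (0.407) |
| 0.5 | −2.00 (0.558) | −2.00 (0.483) | −1.33 (0.455) |
| 0.7 | −2.00 (0.432) | −2.00 (0.398) | −1.33 (0.499) |

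- The first column matches the change-score formula and the second matches the covariate formula. Keeping the admission score as an outcome therefore costs nothing if the arms share a baseline mean.
- The variance ratio is 0.65, 0.75 and 0.85, so the same precision without adjustment needs 54%, 33% and 18% more patients. At rho 0.8 the figures are 0.90 and 11%.
- In the third column the arm coefficient is the mean of three visit differences: (0 − 2 − 2)/3 = −1.33.

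**What the precision difference means.** At SD 7 and rho 0.5 the 95% half-width falls from 1.96×0.558 = 1.09 to 1.96×0.483 = 0.95 points. Power for 2 points rises from 94.8% to 98.5%. Over SD 6 to 8 and rho 0.3 to 0.8, power runs from 75.5% to above 99.9% without adjustment and from 90.8% to above 99.9% with it.

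**Transformation against a raw threshold.** Take the log as an example. A 2-point fall is ln(8/10) = −0.223 from a score of 10, ln(18/20) = −0.105 from 20, and ln(28/30) = −0.069 from 30. Two points have no single equivalent on the transformed scale.

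**The case against.** The case on the other side is strong in several places.

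- **A reader might infer that the SAP has chosen an inefficient analysis.** It has not. It is silent on fixed effects, and an admission score kept as an outcome is fully efficient under a common baseline mean. Even with free baseline means the contrast is unbiased under randomisation. The loss is conditional and concerns efficiency only.
- **A reader might infer the one-third shrinkage from the primary model,** where treatment group is the only fixed effect named. That model is for a single binary outcome. For CAT and E-RS, the difference-in-improvement wording and the day-10 and day-30 rows of Table 2 point towards visit-specific change contrasts. The shrinkage is possible under the text, not planned by it.
- **A reader might infer that a before-after test will replace the randomised comparison.** The paired-tests sentence is general, while the endpoint-specific text names a mixed model every time, and section 10.2.2 uses the word paired to mean repeated measurements. That reading is unlikely. The sentence still conflicts with the model.
- **A reader might infer that skewed scores must be transformed.** Section 10.2.2 offers bootstrapping, which keeps the point scale. What stands is that sections 9 and 10 offer transformation alone and section 10.2.2 does not say which remedy applies.

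It is also fair that these are not key endpoints: Protocol 8.1.2 places CAT and E-RS among the other secondary objectives. The gap itself remains, because a plan compatible with estimates of both 2.0 and 1.33 for the same true effect has not fixed its analysis.

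**Conclusion.** The point holds as a specification gap with a better method available at no cost in data. Without baseline adjustment or a common baseline mean, the standard error is about 5% to 24% larger over rho 0.8 down to 0.3. Under central assumptions that is a modest loss. The more consequential risk is a single arm effect over three visits, which would turn a true 2-point benefit into an estimate of about 1.33 and have it labelled clinically non-significant. The threshold problem arises only if transformation is chosen. The variance ratio depends on assumed correlations and equal variances, and the standard errors and power also on an assumed SD and 315 analysed patients per arm. The factor of two thirds does not depend on SD or rho, but does assume complete data and equal effects at days 10 and 30. Nothing here bears on the primary non-inferiority conclusion.

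**What to change.** In SAP sections 9, 10 and 10.2.2, for CAT and E-RS:

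1. Write the fixed part as arm, visit and arm-by-visit. Either use day 10 and day 30 as outcomes with the admission score (by visit) as covariate, or keep all three visits as outcomes with equal arm means at baseline. Keep the random centre and patient effects.
2. Name the day-10 and day-30 arm differences in raw points as the estimates, put them in the empty effect column of Table 2, and apply the 2-point rule to them.
3. Use bootstrap or robust confidence intervals for non-normal residuals and remove the transformation option.
4. Exempt these endpoints from the general paired-tests and non-parametric sentences in section 9.
5. Reconcile the SAP with the unpaired t-test and Mann-Whitney rule in Protocol section 10.

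The cost is SAP wording and alignment with the protocol. CAT and E-RS are already scheduled at admission, day 10 and day 30, so no new data or patients are needed.

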6.1 General Study Design and Plan

- Study design: prospective, randomized-controlled trial. Patients will be randomized to biomarker-guided treatment (based on blood procalcitonin level) or to usual care. In the usual care arm, and in the biomarker guided-arm in case of high ($> 0.25\mu\text{g/L}$) procalcitonin, patients will receive amoxicillin-clavulanic acid.
- Type of Comparison: non-inferiority.
- Type of control(s): usual care
- Level and method of blinding (e.g. double-blind): The patient and the outcome assessor will be blinded for the allocated treatment strategy. Two independent physicians will be selected per center to be the outcome assessors. The patient will not be blinded for the treatment itself (prednisolone with or without antibiotic therapy).
- Method of treatment assignment: We will use a block-randomisation with randomly alternating blocks of 4 and 6 patients (random permuted block randomisation). The randomisation will be stratified per center.
- At what point in time subjects are randomized relative to treatments, events and study periods: Upon presentation at the emergency department, patients will be clinically

judged for in- and exclusion criteria, among which indication for hospitalization. When eligible the patient will be notified about the study. When the patient is interested in participating, the patient information form will be discussed by the treating physician. The participation being voluntarily and the opportunity to discontinue participation will be made clear by the treating physician. Informed consent will be requested with at least two hours of time to decide

- Sequence and duration of all study periods: screening will occur on the first day of admission as described above, baseline characteristics will be collected within 24 hours of admission, active treatment will be 5 days, follow-up will be 30 days.

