8.4 Missing Data

After signing the informed consent, patients still are allowed to withdraw from the study. Every attempt will be made to collect the primary end-point. Withdrawal by the investigator will mainly be because of safety reasons and mostly constitute a treatment failure.

The statistical analyst will consider all possible reasons for missing data. If it is safe to assume that the data are missing at random (MAR) or missing completely at random (MCAR) we will use multiple imputation for missing values.

Sensitivity analyses will be used to investigate the validity of the MAR assumption against missing not at random (MNAR).

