Length of hospitalization	mean/median days (SD) or [IQR]	mean/median days (SD) or [IQR]		
Time to complete resolution of symptoms (modified Anthonisen criteria)	mean/median days (SD) or [IQR]	mean/median days (SD) or [IQR]		
Re-exacerbation within 30 days	n (%)	n (%)	OR (95% CI)	
EXACT – Respiratory symptoms scale, change: after 10 days after 30 days	mean (SD)or median [IQR]	mean (SD)or median [IQR]		
Non-Invasive ventilation (>72h)	n (%)	n (%)	OR (95% CI)	

Only deviations from the general overview will be noted in the subsequent sub-sections within section 9.

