9.2 Derived variables

The primary endpoint consists of several variables: disease-related mortality, endotracheal intubation, vasopressors, renal failure, lung abscess/empyema, pneumonia development and hospital readmission.

The key secondary endpoint is derived from the scores of the diary card with the modified Anthonisen criteria* the patient will fill in on baseline, day 3, day 5, day 10 and day 30. This endpoint will be scored by an independent physician. If there is incomplete resolution of symptoms, this will result in treatment failure. The symptoms are scored as categorical variables and include shortness of breath (slightly or much worse or 'as baseline condition prior to exacerbation'), sputum production (slightly or much more or 'as baseline condition prior to exacerbation'), sputum discoloration (slightly or strongly increased or 'as baseline condition prior to exacerbation') and minor symptoms as coughing, sore throat, fever, wheezing or a blocked or running nose. When one of these symptoms has not been resolved on day 30 this should result in scoring this as treatment failure.

*Example of the diary card with the modified Anthonisen criteria we used to derive our own diary card in Dutch. This original diary card was designed by Jaap Trappenburg et al. and used in a trial that was published in 2011 [15](Thorax 2011;66:977e984):

After evening diner

Compared with previous weeks ...	DAY 1 _/_/2009	DAY 1 _/_/2009	DAY 1 _/_/2009
I am more short of breath than normal	 No  Yes, slightly increased  Yes, clearly increased	 No  Yes, slightly increased  Yes, clearly increased	 No  Yes, slightly increased  Yes, clearly increased
I produce more sputum than normal	 No  Yes, slightly increased  Yes, clearly increased	 No  Yes, slightly increased  Yes, clearly increased	 No  Yes, slightly increased  Yes, clearly increased

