9.5 Concurrent Illnesses and Medical Conditions

The summary statistics will be produced in accordance with section 9.

10 Efficacy Analyses

- Summary statistics that will be produced for continuous and categorical data:
 - The quality of life endpoints, using the COPD Assessment Test (CAT) and the EXACT-respiratory symptoms questionnaire, consist of multiple (three) measurements per subject. These measurements are all performed on the same time point (baseline, day 10 and day 30). These endpoints will be scored using the mean score and standard deviation when normally distributed and a median with the inter quartile range when the data have a skewed distribution. These data will be analyzed with a mixed effects model with random effects for center and patient to account for the extra hierarchical level in the data. The residuals will be evaluated for normality to test the assumptions of the models. In case of violations, transformations will be conducted on the dependent variable.
 - The unpaired continuous variables will be scored using the mean score and the standard deviation (normal distribution) or the median with the inter quartile range (skewed distribution). These variables will be analyzed using an mixed effects model.
 - The frequency and percentage will be reported for the categorical (mostly dichotomous) variables. Analysis of these variables will be performed using a logistic mixed-effects model.

- Analysis populations that will be used and identification of the primary population.
 - We will analyze the population with a per-protocol analysis and an intention-to-treat analysis. The primary population will be the per-protocol population.

- A statement of the clinical objective rephrased in precise statistical terms (null and alternative hypotheses):
 - Null hypothesis: PCT-guided treatment regarding antibiotic use is inferior to usual care in patients with an acute exacerbation of COPD
 - Alternative hypothesis: PCT-guided treatment regarding antibiotic use is non-inferior to usual care in patients with an acute exacerbation of COPD
- The nature of the hypothesis is confirmatory

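### Time to symptom resolution is analysed as an ordinary continuous variable, with no rule for patients who have not resolved by day 30 or who die first

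*SAP*

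**What the plan says.** SAP 10.2.2 names the endpoint "Time to complete resolution of symptoms in days according to daily symptom diaries evaluating the modified Anthonisen criteria". It classes it as continuous and unpaired, describes it by mean and SD or median and IQR, and gives a mixed-effects model as the test. SAP section 9 (Secondary outcome parameters) sets the same rule for all unpaired continuous variables: "These variables will be analyzed using an mixed effects model". SAP section 10 repeats it. The Table 2 row for this endpoint has only mean or median days.

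Two other rules touch the endpoint. The opening of the secondary-outcome text in SAP section 9 sends skewed data to non-parametric tests. The protocol's Secondary analyses text in section 10 gives the unpaired t-test, or the Mann-Whitney U test if the distribution is skewed.

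On the time horizon, SAP 6.1 states that "follow-up will be 30 days". SAP 9.2 plans for patients who are still symptomatic at that point: "When one of these symptoms has not been resolved on day 30 this should result in scoring this as treatment failure". That sentence defines the separate, binary key secondary endpoint. Disease-related death is part of the primary composite. SAP 8.4 offers multiple imputation if data are missing at random or completely at random, and unspecified sensitivity analyses otherwise.

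**The concern.** A patient who has not resolved by the day-30 assessment has a right-censored time. A patient who dies unresolved has no resolution time at all. A mixed-effects model for a continuous outcome needs a number for each patient. There is one such value per patient, so somebody must decide whether to leave these patients out, set them to 30, rank them last or impute a time. The plan does not decide, so the choice could be made after the data are seen, and it changes the answer.

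The event itself is also open. The documents do not say whether resolution means first or sustained resolution, although re-exacerbation within 30 days is a listed endpoint. A patient who cleared on day 8 and relapsed would be unresolved on day 30 yet have a known first-resolution time.

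The data source is not settled either. Protocol 8.1.2 and SAP 5.2 and 10.2.2 speak of daily diaries. SAP 9.2 has the card filled in at baseline and days 3, 5, 10 and 30, and the footnote to the schedule in protocol 8.3 agrees with that. On the fixed days, a resolution between days 10 and 30 is known only to lie in a 20-day interval.

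**Working it through.** The plan states no figure for this endpoint, so there is nothing to reproduce. The following illustration shows how far the unstated choice can move the result.

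**Inputs**
- 315 per arm (protocol 10.4, SAP 8.5.5); horizon 30 days (SAP 6.1).
- Shares resolved by day 30: assumed, because the documents give none. Two contrasts are used. One is 10 points (70% against 60%). The other is 3.7 points (70% against 66.3%), the size of the only planning contrast in the documents, 20.4% − 16.7% in SAP section 7. That contrast belongs to a different endpoint and is borrowed only for scale.
- Exponential recovery, daily cards, no deaths or losses, no centre effect: all assumed.

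**Formulas.** Let p be the share resolved by day 30, λ = −ln(1 − p)/30 the daily rate, and m the mean time among those resolved.
- m = 1/λ − 30(1 − p)/p
- 30-day restricted mean = p·m + 30(1 − p)

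**Results in days**

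| p | m (resolved only) | restricted mean (all patients) |
|---|---|---|
| 0.70 | 12.06 | 0.70 × 12.06 + 9.00 = 17.44 |
| 0.60 | 12.74 | 0.60 × 12.74 + 12.00 = 19.64 |
| 0.663 | 12.33 | 0.663 × 12.33 + 10.11 = 18.29 |

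- 70% against 60%: the delay over all patients is 19.64 − 17.44 = 2.20; among resolved patients only it is 12.74 − 12.06 = 0.68.
- 70% against 66.3%: 0.84 over all patients and 0.27 among resolved patients.

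The exponential form is not essential. If resolved patients take the same mean time m in both arms and p differs by 0.10, the resolved-only comparison shows 0 and the restricted means differ by 0.10 × (30 − m), which is 1.8 days at m = 12.

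**Power, by simulation** (two-sided 0.05; t-test for the first two columns, Mann-Whitney for the third)

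| Resolved by day 30 | unresolved left out | set to 30 | ranked last |
|---|---|---|---|
| 70% against 60% | about 13% | about 72% | about 75% |
| 70% against 66.3% | about 6% | about 15% | about 16% |

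**Sensitivity to the hazards.** Take Weibull times with shapes 0.9 and 1.2 and 75% resolved in both arms. The restricted means are 15.62 and 17.32, a delay of 1.7 days. Among resolved patients the means are 10.82 and 13.10, so the delay shows as 2.3 days. Power is then about 84% with unresolved patients left out, 52% set to 30 and 54% ranked last. A log-rank test has about 20% here, against about 78% in the 70/60 exponential case. The direction of the error and the ranking of the methods therefore depend on the assumptions.

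**The case against.** Both documents already hold a rank-based route for skewed data, and a rank test that places unresolved patients last would be adequate. On that view the gap is one missing sentence. This stands in part. The route exists, but SAP 10.2.2 prescribes a mixed model for this endpoint, so the two rules conflict, and neither assigns a rank to unresolved patients or deaths.

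SAP 8.4 might be said to cover these patients through imputation. It does not suit them. Being unresolved at day 30 is an observed state rather than a missing value, and a resolution time after death has no clear meaning. The transformation and bootstrap options in SAP 10.2.2 are written for CAT and EXACT only.

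A reader might infer that the plan drops unresolved patients. No text says so. It is one reading of a plan that is silent, and the resolved-only figures above show what that reading would cost. A reader might also take everyone unresolved on day 30 to have a time beyond day 30. That fails for a patient who cleared and relapsed, if first resolution is the event.

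It is also fair that a 10-point contrast is large, which is why 3.7 points is shown beside it. And the unresolved share appears in the same Table 2 as the key secondary endpoint, so a difference in resolution would be visible to readers. That limits the harm but does not say what enters this analysis.

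On the cards, the visit grid in SAP 6.4 and the review of cards at each visit in protocol 8.3 are compatible with daily completion. The conflict lies with SAP 9.2 and the protocol 8.3 footnote.

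**Conclusion.** The point holds. The stated method does not fit a time that is censored at day 30, and no rule covers unresolved patients or deaths. If those patients were left out and recovery were exponential, a 2.2-day delay would show as 0.7 day (70% against 60% resolved) and a 0.84-day delay as 0.27 day (70% against 66.3%). These sizes rest on assumed resolution rates and hazards, complete follow-up and daily cards. The Weibull case shows that the error can go the other way.

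Two stronger conclusions are not supported. The figures do not show that a hazard-ratio model is required, since the log-rank test did worst in the Weibull case. Nor does the trial's main conclusion depend on this: the primary endpoint, the key secondary endpoint and the sample size are unaffected. It should be settled before the data are seen, in proportion to a non-key secondary endpoint.

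**What to change.** 1. Define the event as first or as sustained complete resolution.
2. Replace the entry in SAP 10.2.2 with one prespecified analysis that keeps every patient and allows for centre. Show the cumulative incidence of resolution by arm. Censor patients without the event at their day-30 assessment and losses at the last card, and treat death as a competing event. Summarise by the difference in 30-day restricted mean time to resolution, which does not need proportional hazards. A simpler alternative is a centre-stratified rank test that places patients without the event, and deaths, after day 30.
3. State that these times are not imputed under a missing-at-random assumption.
4. Reconcile the daily diaries with completion at baseline and days 3, 5, 10 and 30. If only the fixed-day cards exist, use the rank test or an interval-censored model, because setting unresolved patients to 30 would tie them with everyone who resolved between days 10 and 30.
5. Align the protocol's Secondary analyses text, SAP sections 9 and 10, and the Table 2 row.

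The cost is wording and a slightly more complex standard analysis. No new data, patients or visits are needed.
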